2.2 ELECTRIC SYSTEM DESCRIPTION

The FreedomFlow[™] Orbital Circumferential Atherectomy System, Electric is a flexible overthe-wire rotary driveshaft used to ablate atherosclerotic plaque from arterial blood vessels within the body. The driveshaft is used together with a compatible introducer sheath and 0.014inch diameter x 300 cm (minimum length) atherectomy guidewire. The driveshaft is introduced into the patient's vasculature by traditional minimally invasive techniques. See Specifications in the 8014 CardioFlow Instruction for Use for information on selecting the appropriate size introducer sheath.

There are two sizes of electric User Handles (H6002 6Fr and H6001 5Fr). Both User Handles will be evaluated in this clinical trial and can be used to treat a range of vessel sizes (2mm to 8mm). Refer to 8014 Cardio Flow Instructions for Use for guidance on appropriate vessel sizes.

The FreedomFlow[™] Orbital Circumferential Atherectomy System - Electric is powered by the Cardio Flow Power Supply H7001, which is a hospital-grade portable, reusable component. H7001 provides DC power to rotate the FreedomFlow[™] driveshaft. H7001 also provides DC

⁰¹⁰⁻⁰⁵⁵ Protocol Version F

power to a saline pump integrated into the electric User Handle. During operation the saline pump delivers saline to the distal tip of the driveshaft.

FreedomFlowTM Orbital Circumferential Atherectomy System - Electric is designed to remove atherosclerotic plaque from peripheral arteries by rotation of diamond-coated spheres mounted eccentrically on a coiled driveshaft. The electric User Handle is used to activate rotation and advance the driveshaft on a commercially available 0.014-inch atherectomy guidewire. The guidewire and introducer sheath are not included with the system. The electric User Handle is the only part of the system applied to the patient.

2.2.1 Electric User Handle

The electric User Handle is a single-use component that provides control over rotation and translational movement of the integrated driveshaft. The User Handle is supplied sterile (via Ethylene Oxide gas). A button on the User Handle is depressed to activate the driveshaft and released to stop rotation. The carriage of the User Handle has 12 cm of travel and is used to advance and retract the driveshaft's diamond-coated distal tip and eccentrically mounted diamond-coated spheres independently of the catheter tubing. The User Handle guidewire clamp prevents guidewire movement during use. There are two sizes of electric User Handles (H6002 6Fr and H6001 5Fr). Both electric User Handles will be evaluated in this clinical trial and can be used to treat a range of vessel sizes (2mm to 8mm). Refer to 8014 Cardio Flow Instructions for Use for guidance on appropriate vessel sizes.

[figure not shown]

Figure 2-5: FreedomFlow[™] Orbital Atherectomy System - Electric¹

2.3 DRIVESHAFT DETAILS

The driveshaft is a hollow multi-strand cable that drives the spinning of the diamond-coated spheres. The off-axis eccentric attachment of the spheres onto the driveshaft force the spheres in an outward centrifugal direction during rotation. The diamond-coated distal tip is designed to add stability and may ease transition into a tight stenotic lesion. The driveshaft of User Handles H3001 and H6002 have 5 diamond coated spheres with the largest sphere 2 mm in diameter. The

¹ Item 1 is the reusable Power Supply. User Handle and Saline Infusion Tubing Set are listed as Items 2-12.

⁰¹⁰⁻⁰⁵⁵ Protocol Version F

driveshaft of User Handles H4001 and H6001 have 5 same size (1.5 mm in diameter) diamond coated spheres.

H4001 and H6001 – 5 French compatible

H3001 and H6002 – 6 French compatible

Figure 2-6: Driveshaft Configurations

2.4 INTENDED USE

The FreedomFlowTM Orbital Circumferential Atherectomy System is a minimally invasive, catheter-based system designed for improving luminal diameter and modifying vessel wall compliance in patients with PAD.

2.5 INDICATION FOR USE

The FreedomFlowTM Orbital Circumferential Atherectomy System is indicated to remove atherosclerotic plaque and modifying vessel wall compliance within peripheral arterial vessels. The therapy is intended for patients who are acceptable candidates for percutaneous transluminal atherectomy.

3 STUDY PURPOSE AND OBJECTIVE

The objective of the study is to evaluate the safety and effectiveness of the FreedomFlowTM Orbital Circumferential Atherectomy System for atherosclerotic plaque removal and vessel modification in *de novo* target lesions in the peripheral vasculature of the lower extremities.

4 STUDY DESIGN

4.1 OVERVIEW

The FAST II study is a prospective, multi-center, non-randomized single-arm study designed to evaluate the safety and effectiveness of the FreedomFlow[™] Orbital Circumferential Atherectomy System in subjects diagnosed with peripheral arterial disease of the lower extremities.

⁰¹⁰⁻⁰⁵⁵ Protocol Version F

4.2 SAMPLE SIZE AND NUMBER OF CENTERS

The study may enroll up to 112 subjects and will be conducted at up to 15 investigational sites in the United States. Approximately 56 subjects will be enrolled using the pneumatic system and 56 subjects will be enrolled using the electric system.

4.3 STUDY DURATION

Enrollment is expected to take approximately 12 months with observation periods at time of procedure, pre-discharge, 30 days, and 6 months post-procedure follow-up.

5 STUDY ENDPOINTS

5.1 PRIMARY EFFECTIVENESS ENDPOINT

The primary effectiveness endpoint is technical Success defined as the ability of the Cardio Flow FreedomFlowTM Orbital Circumferential Atherectomy System to achieve a residual diameter stenosis \leq 50% without adjunctive therapy, as assessed by an independent Angiographic Core Laboratory.

5.2 PRIMARY SAFETY ENDPOINT

The primary safety endpoint is freedom from a composite of new onset major adverse events (MAE) through 30-day follow-up as adjudicated by an independent clinical events committee (CEC).

The components of the MAE are defined as:

- 1. Cardiovascular related death: All cardiovascular cause mortality.
- 2. **Myocardial infarction (MI):** Any newly diagnosed MI post procedure, defined as CK-MB ≥2X upper limit normal (ULN).
- 3. Clinically driven target lesion revascularization (TLR): any repeat percutaneous or surgical intervention to treat objectively documented symptoms of recurrent ischemia attributable to the treated lesion.
- 4. **Clinically significant target vessel dissection:** NHLBI grade C or greater as confirmed by angiography.
- 5. Clinically significant target vessel perforation: NHLBI Type III as confirmed by angiography.
- 6. **Unplanned major target limb amputation:** Amputation of the transmetatarsals or higher that was not previously planned as part of the overall treatment strategy.

- 7. **Clinically relevant distal embolization:** Emboli requiring surgical or medical intervention and/or the presence of symptoms.
- 8. **Pseudoaneurysm:** disruption/weakening of the arterial wall at the treatment site as confirmed by angiography.

5.3 SECONDARY ENDPOINTS

- 1. Clinical success, defined as \leq 50% residual stenosis at target lesion with or without adjunctive therapy, as assessed by an independent Angiographic Core Laboratory.
- 2. Procedure success, defined as ≤50% residual stenosis at target lesion with or without adjunctive therapy, no procedure-related MAE, no device malfunction causing the procedure to be aborted.
- 3. Improvement of ABI at 30 days and 6 months.
- 4. Improvement of Rutherford Classification at 30 days and 6 months.
- 5. Improvement of patient reported outcomes (PRO, VascuQoL questionnaire) at 30 days and 6 months.
- 6. Clinically driven target lesion revascularization (TLR) at 6 months, target vessel revascularization (TVR) at 30 days and 6 months (as assessed by an independent Angiographic Core Laboratory).
- 7. Primary patency, primary assisted patency and secondary patency at 30 days and 6 months. Patency will be evaluated by duplex ultrasound and evaluated by an independent Vascular Ultrasound Core Laboratory. The restenosis is defined as PSVR of 2.5.

6 STUDY PROCEDURE

6.1 PATIENT ELIGIBILITY, PRE-SCREENING AND EXCLUSIONS

All patients scheduled for a percutaneous endovascular intervention for PAD in the lower extremity will be screened for study eligibility. A Screening/Enrollment Log will be provided to the study sites, in order to maintain a cumulative tracking of all screened patients.

Subjects must meet all inclusion/exclusion criteria for enrollment in the clinical study. Reasons for screening failure(s) will be documented.

6.1.1 Inclusion Criteria

Subjects must meet ALL of the following criteria to be eligible for participation in the study:

- 1. Age \geq 18 years old.
- 2. Subject is a candidate for percutaneous endovascular intervention for peripheral vascular disease in the lower extremity.
- 3. Objective hemodynamic evaluation that subject has a resting ankle-brachial index (ABI) $\leq 0.90 \text{ } \underline{\textbf{OR}}$ a resting toe-brachial index (TBI) of $\leq 0.80 \text{ } \underline{\textbf{OR}}$ ankle pressure of $\leq 70 \text{ mmHg}$.
- 4. Clinical presentation of lifestyle limiting claudication, rest pain and/or ischemic wound as characterized by Rutherford Classification 2, 3, 4, or 5.
- 5. Disease is located in the common femoral, superficial femoral, popliteal, tibioperoneal, anterior tibial, posterior tibial, or peroneal arteries.
 - a. De novo target lesion(s) with stenosis \geq 70% by visual estimation and/or
 - b. Lesion(s) treated by percutaneous transluminal angioplasty (PTA) and/or atherectomy ≥ 3 months prior with a restenosis ≥70% by visual estimation.
 - c. Up to three lesions can be treated at the index procedure provided the cumulative total lesion length is ≤ 20 cm AND all lesions are in the same target leg.
- 6. Target reference vessel diameter (proximal and distal to target lesion) is 2 to 8 mm by angiographic visual estimation.
- 7. At least one patent vessel run-off to the ankle or foot at baseline.
- 8. The target lesion(s) can be successfully crossed with a commercially available 0.014" atherectomy guidewire without any complications during wiring procedure.
- 9. Subject signs a written Informed Consent form to participate in the study, prior to any study mandated determinations or procedure.

6.1.2 Exclusion Criteria

Subjects must be EXCLUDED from participation in this study if ANY of the following criteria are met:

- 1. Is female with childbearing potential not taking adequate contraceptives or is currently breastfeeding.
- 2. Target lesion is within a native graft or synthetic graft.
- 3. Target lesion is an in-stent restenosis.
- 4. Target lesion is a Chronic total occlusion (CTO) with occlusion length greater than 10 cm and/or with wire crossed sub-intimally. CTO wire placement in true lumen must be confirmed via IVUS prior to enrollment.
- 5. Subject has significant stenosis or occlusion of inflow tract (upstream disease) not successfully treated during the index procedure or prior to treatment of the target lesion.

- 6. Intra-operative (intra-procedure) clinical or angiographic complication (other than non-flow limiting dissections) attributed to the use of a currently marketed device prior to introduction of the Cardio Flow atherectomy driveshaft.
- 7. Evidence or history of aneurysmal target vessel.
- 8. Clinical/angiographic evidence of distal embolization prior to intervention.
- 9. History of an endovascular procedure or open vascular surgery on the index limb within 30 days prior to the index procedure (other than treatment of inflow tract disease). Endovascular procedure or open vascular surgery on the non-index limb cannot be staged within 2 weeks prior to the index procedure.
- 10. Planned endovascular or surgical procedure prior to the patient's 30 day follow up.
- 11. Signs and symptoms of systemic infection (temperature of $\geq 38.0^{\circ}$ Celsius and WBC of $\geq 12,000$ cells/µL) at the time of assessment; Note: If infection is adequately treated and controlled patient may be enrolled.
- 12. Unstable coronary artery disease or other comorbid condition(s) that, in the judgment of the physician precludes safe percutaneous intervention.
- 13. Significant acute or chronic kidney disease with a creatinine level > 2.5mg/dL and/or requiring dialysis.
- 14. Evidence or history of intracranial or gastrointestinal bleeding, intracranial aneurysm, myocardial infarction or stoke within 2 months of index procedure.
- 15. Known allergy to contrast agents or medications used to perform endovascular intervention that cannot be adequately pre-treated.
- 16. Subjects in whom anti-platelet, anticoagulant, or thrombolytic therapy is contraindicated.
- 17. Heparin-induced thrombocytopenia (HIT) not able to use Bivalirudin.
- 18. Uncorrectable bleeding diathesis, platelet dysfunction, thrombocytopenia with platelet count less than 125,000/mm², known coagulopathy, or INR > 1.8.
- 19. Evidence of thrombus within target lesion or thrombolytic therapy within 2 weeks of the index procedure.
- 20. Has life expectancy < 12 months in the opinion of the investigator.
- 21. Subject is unwilling or unable to comply with the follow-up study requirements.
- 22. Subject is currently participating in an investigational drug or another investigational device exemption (IDE) study.

6.2 PRE-SCREENING AND WRITTEN INFORMED CONSENT

The site may pre-screen potential subjects by reviewing medical records to identify the study population. Once identified these subjects are approached for the study and consented. The site

⁰¹⁰⁻⁰⁵⁵ Protocol Version F

may not initiate any study specific (non-standard of care) procedures without first obtaining informed consent

Subjects who pass the initial pre-screening will be asked to sign the study specific IRB approved Informed Consent. A member of the research team will approach the subject to obtain informed consent. The background of the proposed study, the procedure, the follow-up schedule and all potential benefits and risks will be carefully explained to the subject prior to obtaining the potential subject's informed consent. A subject is considered "Enrolled" after signing the study specific Informed Consent and if he/she meets all inclusion and exclusion criteria.

Informed consent will be obtained prior to any study specific screening/baseline tests are performed. This does not include any procedures or tests that are obtained via the standard of care related to the subject's non-study related care, prior to undergoing the index procedure.

6.3 ENROLLMENT

Only subjects who meet the inclusion/exclusion criteria, and provide consent will be eligible to receive the treatment and participate in the study. A subject will be considered officially enrolled only if the subject has signed informed consent, meets all the inclusion and none of the exclusion criteria and the investigational device is attempted. A 25% enrollment ceiling per site will be implemented.

6.4 BASELINE EVALUATION (WITHIN 30 DAYS OF INDEX PROCEDURE)

Subjects that meet the pre-screening eligibility criteria and signed informed consent will have the following collected. These evaluations can occur anytime within 30 days of the procedure to the day of treatment. Only one angiogram is required.

- Demographic Information: race, age, weight, height
- Medical History / Current Status
- Physical Exam and Vital Signs
- Angiogram (recorded and sent to sponsor and core lab)
- Duplex Ultrasound (if available, recorded and sent to sponsor and core lab)
- Rutherford Classification
- Laboratory Assessments:
 - CBC, creatinine, and potassium
 - INR & PT if subject is on chronic warfarin therapy (on day of procedure)
 - Urine pregnancy test if female of child-bearing potential (within 7 days of procedure)
- VascuQoL Questionnaire

- Ankle Brachial Index (ABI) and/or Toe Brachial Index (TBI)
- Concomitant Medications

6.5 INDEX PROCEDURE

Subjects who meet all of the eligibility criteria will have their scheduled index procedure performed in accordance with physician/investigational site standard practices.

6.5.1 Angiography

Prior to or up to the time of the index procedure, standard angiography will be performed per the guidelines established by the Angiographic Core Laboratory, to confirm final anatomic eligibility. Subjects who do not meet the final angiographic eligibility criteria, as determined by the investigator at the time of the procedure, will be documented as angiographic screen failures and will not be considered enrolled in the study and no further data will be collected. A subject is considered as "enrolled" after the subject meets all angiographic criteria and a atherectomy 0.014" guidewire successfully crosses the target lesion via the true vessel lumen.

Angiography will be performed throughout the procedure to document the treatment outcomes and sent to the sponsor. At a minimum, angiographic images at the following timepoint should be taken.

- Baseline angiography to determine subject's eligibility.
- Following treatment of any lesions that are pre-dilated by balloon angioplasty if performed.
- After the Cardio Flow FreedomFlowTM orbital circumferential atherectomy treatment session(s).
- Post any adjunctive interventions, e.g. balloon angioplasty and/or stenting, to optimize the outcome or bailout the procedure due to vascular complications.
- Final angiography prior to the end of the procedure.

Up to 3 target lesions are allowed based on the angiographic criteria by this protocol. If 2 or 3 target lesions are selected, the lesion will be numbered based on the anatomic order, i.e. common femoral artery, proximal, middle or distal segment of superficial femoral artery, P1, P2 or P3 segment of popliteal artery, anterior tibial artery, posterior tibial artery, and peroneal artery, regardless of the treatment order.

6.5.2 Non-Target Lesion Intervention

If a non-target lesion(s) is located at the iliac artery or at the femoral artery with a vessel size greater than 8 mm in diameter in the target limb and requires intervention during the index procedure, the lesion(s) MUST be treated with commercially available devices prior to the Cardio Flow FreedomFlowTM orbital circumferential atherectomy procedure. The Cardio Flow FreedomFlowTM orbital circumferential atherectomy procedure can be performed ONLY if there are no angiographic complications at the non-target vessel/lesion site or in downstream

⁰¹⁰⁻⁰⁵⁵ Protocol Version F

vasculatures, and no observed clinical adverse events. If any angiographic complication at the non-target vessel/lesion site and/or downstream vasculatures or a clinical adverse event occurred, the subject MUST not proceed to the Cardio Flow FreedomFlowTM orbital circumferential atherectomy procedure. The subject will be considered as an angiographic screening failure.

If a non-target lesion(s) located at the target limb does not require an immediate attention, it can be staged and treated with any commercially available devices greater than 30 days post the index procedure after the 30-day study assessment.

If a non-target lesion(s) is at non-target limb, it may be treated either at least a week prior to the index procedure without on-going adverse event at the time of enrollment or 30 days post the index procedure after the 30-day study assessment.

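### Protocol 6.5.2 allows treatment of the other leg from one week before the index procedure, but mandatory exclusion 9 bars it within two weeks, so the 6.5.2 permission is wrong for gaps of 7 to 13 days

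*Protocol*

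**What the plan says.** Protocol 6.5.2 covers lesions other than the target lesion. For one in the other limb it offers two time slots. Before the index procedure, "it may be treated either at least a week prior to the index procedure", on the sole further condition that no adverse event is ongoing at enrolment. After it, "or 30 days post the index procedure after the 30-day study assessment".

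Exclusion criterion 9 has two sentences, worded the same in the synopsis and in 6.1.2. The first bars procedures on the index limb in the preceding 30 days and carries an exception for inflow-tract disease. The second reads "Endovascular procedure or open vascular surgery on the non-index limb cannot be staged within 2 weeks prior to the index procedure" and carries no exception.

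Four places fix the standing of the exclusion criteria:

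- 6.1: "Subjects must meet all inclusion/exclusion criteria for enrollment in the clinical study".
- Lead-in to 6.1.2: "Subjects must be EXCLUDED from participation in this study if ANY of the following criteria are met".
- 6.3: "Only subjects who meet the inclusion/exclusion criteria, and provide consent will be eligible to receive the treatment and participate in the study".
- 6.5, which opens the section containing 6.5.2: "Subjects who meet all of the eligibility criteria will have their scheduled index procedure performed".

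For the secondary point, Protocol 8.2 and SAP 5 define ITT as consented subjects who satisfy every inclusion criterion and no exclusion criterion. They define mITT as the ITT subjects in whom the device was attempted, and PP as the mITT subjects without major protocol deviations. Protocol 12.9 gives enrolment of a subject who fails the criteria as its example of a major violation.

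**The concern.** The two rules govern the same event, a vascular procedure on the other leg before the index procedure, and set different minimum gaps. Section 6.5.2 is where an operator planning staged treatment of both legs would look. It gives an explicit permission and does not point to exclusion 9. A site that relied on it with, say, a 10-day gap would treat a subject whom the protocol excludes.

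What is at stake is eligibility compliance. The route from an ineligible subject to the primary analysis is a separate matter, and it would arise for any eligibility violation. Under the literal ITT and mITT definitions, a treated subject found ineligible afterwards leaves the primary analysis of a single-arm trial, possibly once the outcome is known.

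**Working it through.** **Timing rules, day by day.** Let g be the whole number of days from the non-target-limb procedure to the index procedure. Section 6.5.2 permits g ≥ 7. Exclusion 9 bars g < 14, or g ≤ 14 if within 2 weeks is read to include day 14.

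| Gap g (days) | 6.5.2 | Exclusion 9 | Conflict |
|---|---|---|---|
| 0 to 6 | not permitted | barred | no |
| 7 to 13 | permitted | barred | yes, 7 values |
| 14 | permitted | depends on reading | only if inclusive |
| 15 or more | permitted | not barred | no |

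**Possible reconciliations.** The inflow-tract exception belongs to the index-limb sentence of exclusion 9, so it does not reach the other limb. The adverse-event condition in 6.5.2 does not change the interval. No other text links the two windows.

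**Which text gives way.** The provisions in 6.1, 6.1.2, 6.3 and 6.5 all require the criteria to be met before treatment, and 6.5.2 sits beneath 6.5. Exclusion 9 therefore governs.

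**Extent of the error.** It is confined to the pre-procedure slot. The post-procedure slot agrees with exclusion 10 ("Planned endovascular or surgical procedure prior to the" 30-day follow-up).

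**Effect on the design figures.** None. The sample size of 112, the one-sided 0.025 level, and the goals of 85% (safety) and 86% (effectiveness) do not depend on this interval.

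**Secondary point, conditional on exactly one treated subject being removed from an mITT set of 112.** The Clopper-Pearson two-sided 95% lower bound for x successes in n is the 0.025 quantile of Beta(x, n − x + 1).

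| Endpoint (goal) | All 112 kept | One failure removed |
|---|---|---|
| Safety (85%) | 102/112, bound 84.2%, fails | 102/111, bound 85.2%, passes |
| Effectiveness (86%) | 103/112, bound 85.3%, fails | 103/111, bound 86.3%, passes |

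These are the only counts at which removing one failure changes the conclusion. With one success more, the full set already passes (103/112 gives 85.3% against 85%; 104/112 gives 86.4% against 86%). Removing one success changes no conclusion.

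If the removed subject has average risk, the chance of a change is P(k failures in 112) × k/112:

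- Safety, planned failure rate 5%: 0.0295 × 10/112 = 0.26%.
- Effectiveness, planned failure rate 4%: 0.0215 × 9/112 = 0.17%.
- True rate of 92% on either endpoint (an illustrative assumption): 0.123 × 10/112 and 0.137 × 9/112, about 1.1% each.

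The documents give no probability that a subject would be removed, so these are not unconditional risks. They say nothing about the 7-to-13-day gap.

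**The case against.** The strongest reply is that the protocol already resolves the conflict. Every route to treatment passes through the exclusion criteria, 6.5.2 sits under a sentence limiting the procedure to eligible subjects, and Protocol 10.1.2 lets monitors verify eligibility. Harm requires a site to read 6.5.2 in isolation. This stands as a limit on the weight of the point, but it does not make the text right. It tells a reader which rule wins, while 6.5.2 still grants the losing permission. The monitoring it relies on may come late, since 10.1.2 anticipates at least one visit per site once that site's 30-day follow-up is complete.

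On the secondary point, the reply is that the PP definition, read with 12.9, suggests ineligible treated subjects were expected to stay in mITT and leave only at PP. That is a fair reading of intent. The literal ITT wording says otherwise, so the definitions conflict with each other.

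Three stronger readings might be inferred, and the documents do not support them:

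- *Sites have already been confused by this rule.* The revision history records that Version C reworded exclusion 9 for clarity at sites' request. It does not say which part, and the index-limb rule or the inflow exception could equally have prompted it.
- *Exclusion 9 itself needs rewriting to settle day 14.* Its use of within is ordinary wording, repeated in other criteria. Replacing it with less than 14 days would loosen the criterion if the inclusive sense was meant.
- *The timing conflict threatens the primary result.* The figures above concern removal of a subject for any eligibility violation and assume that one such removal occurs.

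**Conclusion.** The inconsistency is real and is in the current Version F text. The pre-procedure permission in 6.5.2 is wrong for gaps of 7 to 13 days, seven whole-day values. It is a minor correction to an operative rule, worth making because an explicit permission leads to what the protocol itself classes as a major violation. The number of subjects affected is unknown and may be zero.

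The conclusion rests on taking non-target limb and non-index limb as the same limb, and on the mandatory status of the exclusion criteria. The documents do not say which interval was clinically intended. They establish only which one governs.

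The analysis-set conflict also holds, as a separate and secondary point. Any bias from dropping a single treated subject could run only towards meeting a goal, and would be small under the conditions stated.

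**What to change.** **Timing.** In 6.5.2 only, replace the one-week condition with: *more than 2 weeks before the index procedure (see exclusion criterion 9)*. Leave exclusion 9 as it is. More than 2 weeks satisfies exclusion 9 on either reading of day 14.

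The cost is a one-phrase protocol amendment with IRB approval and a notice to up to 15 sites, and it can travel with any other amendment. Where clinically acceptable, a subject in the gap can be postponed rather than lost, by at most 15 − 7 = 8 days. The 30-day baseline window in 6.4 must still be met. The pregnancy test (within 7 days of the procedure) and the INR and PT for subjects on warfarin (day of procedure) may need repeating.

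**Analysis sets (separate).** In Protocol 8.2 and SAP 5, define mITT as all consented subjects in whom the device was attempted, and remove eligibility violations only in the PP set. SAP 6.4 reports adverse events on the ITT set, so it should be pointed at the redefined mITT set. Otherwise these treated subjects would still be missing from the safety tables. This is a small amendment to both documents.

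Neither change touches the sample size, endpoints or performance goals.
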